## 5.8 Off Study Criteria

Patients can be taken off study at any time at their own request, or they may be withdrawn at the discretion of the investigator for safety, behavioral or administrative reasons. The reason(s) for discontinuation from study will be documented and may include:

- Patient withdraws consent (termination of treatment and follow-up);
- Loss of ability to freely provide consent through imprisonment or involuntary incarceration for treatment;
- Patient is unable to comply with protocol requirements;
- Treating physician judges continuation on the study would not be in the patient's best interest;
- Patient becomes pregnant (pregnancy to be reported along same timelines as a serious adverse event);
- Development of second malignancy (except for basal cell carcinoma or squamous cell carcinoma of the skin) that requires treatment which would interfere with this study;
- Lost to Follow-up. If a research subject cannot be located to document survival after a period of 2 years, the subject may be considered "lost to follow-up." All attempts to contact the subject during the two years must be documented
- Termination of the study by The University of Michigan;
- Patient completes protocol treatment and follow-up criteria.

## 6.0 STUDY PROCEDURES

### 6.1 Screening/Baseline Procedures

Assessments performed exclusively to determine eligibility for this study will be done only after obtaining informed consent. Assessments performed for clinical indications (not exclusively to determine study eligibility) may be used for baseline values even if the studies were done before informed consent was obtained.

### 6.2 Time and Events Table

All screening labs must be performed within 14 days prior to registration unless otherwise stated. Baseline imaging must be obtained within 28 days prior to registration.

	Screening*	Cycle 1 Day 1	Day 1 All Cycles n	Day 8, Cycles 1 and 2** n	Day 15 All Cycles n	Off Treatment n	Follow -Up m
Olaparib a		X	X-----	X-----	X-----		
Trabectedin		X	X				
Informed Consent	X						
History, vitals and PE	X	X	X			X	
Height & Weight b							
ECOG Performance Status	X	X	X			X	
ECG	X						

Concomitant medication review	X	X	X				
Toxicity Evaluations		X	X-----X				
Tumor Measurements c	X		X c			X	
CBC w/diff, PLT d	X	X	X	X	X	X	
Serum Chemistry e	X	X	X	X	X	X	
APTT, INR f	X						
Creatine phosphokinase	X	X	X			X	
Urinalysis g	X						
B-HCG h	X	X	X			X	
Transthoracic echocardiogram i	X		X i (every 3 cycles)				
Cardiovascular Biomarkers j	X		X j (C3D1 only)				
Archival Tissue k	X						
Bone marrow or blood cytogenetic samples l							

a. Olaparib is administered with continuous twice daily dosing
 
b. Vitals = temperature, pulse, respirations, blood pressure.
 
c. CT and/or MRI scans to cover bodily areas in which there is disease or suspected disease. Baseline scans to be obtained within 28 days of registration. Restaging scans will be repeated at C3D1 (<math>\pm 7</math> days) then every 3 cycles (<math>\pm 7</math> days) until disease progression. If clinical concerns for progression or significant delays in cycle length, imaging assessment may be obtained early at the discretion of the treating physician and continued at an interval of every 3 cycles at minimum. Scans should be obtained at the end of treatment visit if there is no prior radiographic confirmation of disease progression. The same method of assessment (i.e. CT, MRI) and the same technique should be used to characterize each identified and reported lesion at baseline and during follow-up. RECIST 1.1 guidelines will be used.
 
d. Hematology: CBC with differential to include WBC, hemoglobin, platelet count, absolute neutrophil count, absolute lymphocyte count and mean cell volume
 
e. Albumin, alkaline phosphatase, total bilirubin, bicarbonate, BUN, calcium, chloride, creatinine, glucose, potassium, total protein, SGOT (AST), SGPT (ALT), sodium
 
f. Activated partial thromboplastin time (APTT) and International normalized ratio (INR) will be performed at screening and if clinically indicated. For patients on warfarin it is recommended that INR monitored at least weekly for the first cycle and then on day 1 of each cycle thereafter, if stable. Each coagulation test result will be recorded in CRF.
 
g. Urinalysis to include measurement of hemoglobin/red blood cells/ or blood, protein or albumin, and glucose
 
h. Pregnancy tests on blood or urine samples will be performed for women of childbearing potential within 28 days prior to the start of study treatment, on Day 1 of the study prior to commencing treatment and at start of each cycle and at the 30 day follow up visit. Tests will be performed by the hospital's local laboratory. If results are positive the patient is ineligible/must be discontinued from study treatment immediately. Details of the pregnancy tests must be recorded in the patient's medical records.
							

- i. Transthoracic echocardiogram (TTE) will be obtained at baseline to ensure adequate LVEF. Repeat TTE will be obtained every 3 cycles ( $\pm 1$  cycles) while on trabectedin or if clinical concern of decline in ejection fraction. MUGA can be performed if inadequate assessment by TTE per standard practice.
- j. Assessment of cardiovascular biomarkers including suPAR, BNP, high-sensitive troponin-I and high-sensitivity CRP will be obtained at baseline and after 2 doses of trabectedin on cycle 3 day 1.
- k. Results of NGS (if available) and archival tumor tissue to test for the presence of alterations in DNA repair pathways. Patients will not be asked to undergo an additional biopsy to obtain tumor sample. Full reports must be provided by the investigator for documentation on the Patient Safety database. These data are not required to be entered into CRF.
- l. Bone marrow or blood cytogenetic samples may be collected for patients with prolonged hematological toxicities at any timepoint as clinically indicated as defined in Section 5.2. Bone marrow analysis should include an aspirate for cellular morphology, cytogenetic analysis and flow cytometry, and a core biopsy for bone marrow cellularity. If it is not possible to conduct cytogenetic analysis or flow cytometry on the bone marrow aspirate, then attempts should be made to carry out the tests on a blood sample.
- m. Patients will be followed every 3 months via phone for documentation of progression and survival status for a minimum of 2 years from registration. If patient is unavailable, then survival status will be determined if possible, by public available information.
- n. Visits on day 1 of each cycle, lab measurements at days 1, 8 and 15 of each cycle, and the end of treatment visit, can be completed  $\pm 3$  days.

\* Screening labs to be obtained within 14 days of initiation of therapy. Baseline imaging to be obtained within 28 days of initiation of therapy.

\*\* Laboratory assessment will be done on day 8 for first 2 cycles to monitor for cytopenias.

Continued day 8 laboratory assessment beyond cycle 2 is at the discretion of the treating physician.

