### 3.1 Inclusion Criteria

- 3.1.1 Advanced unresectable or metastatic sarcoma
  - Cohort 1: LMS/LPS
  - Cohort 2: Other histologies (excluding Gastrointestinal Stromal Tumors)
- 3.1.2 Must have received at least 1 prior standard systemic therapy regimen. For cohort 1 patients, this must have included a prior anthracycline.
- 3.1.3 Measurable disease by RECIST 1.1 criteria
- 3.1.4 Age  $\geq$  16 years
- 3.1.5 ECOG  $\leq$  1
- 3.1.6 Adequate hematologic, renal and hepatic function within 14 days prior to administration of study treatment as defined below:

Hemoglobin	$\geq 10$ g/dL with no blood transfusion within 28 days
Absolute neutrophil count	$\geq 1.5 \times 10^9$ /L
Platelets	$\geq 100 \times 10^9$ /L

Total Bilirubin	$\leq 1.5 \times$ institutional upper limit of normal (ULN).  NOTE: patients with elevated bilirubin secondary to Gilbert's disease are eligible to participate ( $<2.0 \times$ ULN should be used)
Aspartate aminotransferase (AST) & alanine aminotransferase (ALT)	$\leq 2.5 \times$ institutional ULN unless liver metastases are present in which case AST and ALT must be $\leq 5 \times$ ULN
Serum creatinine	Estimated or calculated creatinine clearance (Cockcroft-Gault formula) $\geq 51$ mL/min using the Cockcroft-Gault equation or based on a 24-hour urine test:  Estimated creatinine clearance = $(140 - \text{age} [\text{years}]) \times \text{weight} (\text{kg}) \times F^a$ serum creatinine (mg/dL) $\times 72$ a where F=0.85 for females and F=1 for males.

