## 5.0 TREATMENT PLAN

### 5.1 Treatment Dosage and Administration

Protocol treatment must start within 14 business days of registration to the study.

Trabectedin 1.1 mg/m^2 will be administered intravenously over a 24-hour continuous infusion once every 21 days. Actual body weight from screening will be used to calculate dose. If weight changes by more than 10% from baseline, recalculate the dose.

Olaparib 150 mg tablets will be taken orally twice daily with a cycle length of 21 days. Olaparib should be taken at the same time every day, 12 hours apart with one glass of water. Olaparib can be taken with or without food. Tablets should be taken whole, not crushed or mixed into food. It is prohibited to consume grapefruit juice while on olaparib therapy. If vomiting occurs shortly after the olaparib tablets are swallowed, the dose should only be replaced if all of the intact tablets can be seen and counted. Should any patient enrolled on the study miss a scheduled dose for whatever reason (e.g., as a result of forgetting to take the tablets or vomiting), the patient will be allowed to take the scheduled dose up to a maximum of 2 hours after that scheduled dose time. If greater than 2 hours after the scheduled dose time, the missed dose is not to be taken and the patient should take their allotted dose at the next scheduled time.

Patients will be requested to maintain a medication diary of each dose of medication. The medication diary should be returned and/or reviewed by clinic staff at each scheduled clinic visit during the course of treatment.

REGIMENT DESCRIPTION					
Agent	Pre-medications; Precautions	Dose	Route	Schedule	Cycle Length
Trabectedin	Pre-medicate with dexamethasone 20 mg IV approximately 30 min prior to trabectedin. Pre-medicate with palonosetron 0.25 mg IV (or similar anti-emetic per institutional guidelines) prior to trabectedin	1.1 mg/m 	IV continuous infusion over 24 hours (+/- 2 hours)	Day 1	3 weeks (21 days)
Olaparib	It is prohibited to consume grapefruit, grapefruit juice and Seville oranges for duration of therapy. No routine prophylactic anti-emetic treatment is	150 mg	PO	BID, continuous	

	required; however, patients should receive appropriate anti-emetics in accordance with local treatment practice guidelines. Alternatively, olaparib tablets can be taken with a light meal/snack (i.e. 2 pieces of toast or biscuits).				
--	--	--	--	--	--

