#### 7.1.3 Guidelines for Evaluation of Measurable Disease

All measurements should be recorded in metric notation, using calipers if clinically assessed. All baseline evaluations should be performed as close as possible to the treatment start and never more than 4 weeks before the beginning of the treatment.

The same method of assessment and the same technique should be used to characterize each identified and reported lesion at baseline and during follow-up. Imaging based evaluation should always be done rather than clinical examination unless the lesion(s) being followed cannot be imaged but are assessable by clinical exam.

**Clinical lesions:** Clinical lesions will only be considered measurable when they are superficial and >10mm diameter as assessed using calipers (e.g. skin nodules). For the case of skin lesions, documentation by color photography including a ruler to estimate the size of the lesion is suggested. As noted above, when lesions can be evaluated by both clinical exam and imaging, imaging evaluation should be undertaken since it is more objective and may also be reviewed at the end of the study.

**Chest X-ray:** Chest CT is preferred over chest X-ray, since CT is more sensitive than X-ray, particularly in identifying new lesions. However, lesions on chest X-ray may be considered measurable if they are clearly defined and surrounded by aerated lung.

**CT, MRI:** CT is the best currently available and reproducible method to measure lesions selected for response assessment. This guideline has defined measurability of lesions on CT scan based on the assumption that CT slice thickness is 5mm or less. When CT scans have slice thickness greater than 5 mm, the minimum size for a measurable lesion should be twice the slice thickness. MRI is also acceptable in certain situations (e.g. for body scans).

**Ultrasound:** Ultrasound is not useful in assessment of lesion size and should not be used as a method of measurement. If new lesions are identified by ultrasound in the course of the study, confirmation by CT or MRI is advised. If there is concern about radiation exposure at CT, MRI may be used instead of CT in selected instances.

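### The baseline imaging window is counted from registration in two places and from treatment start in two others, so a scan that meets the registration rule can be 46–48 days old at first dose

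*Combined protocol and SAP*

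**What the plan says.** Four statements set the age of the baseline scan.

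- Section 6.2, lead-in: "Baseline imaging must be obtained within 28 days prior to registration".
- Section 6.2, footnote c: "Baseline scans to be obtained within 28 days of registration".
- Section 6.2, asterisk footnote: "Baseline imaging to be obtained within 28 days of initiation of therapy".
- Section 7.1.3: baseline evaluations are to be "never more than 4 weeks before the beginning of the treatment".

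The two anchors are not the same day. Section 5.1 states: "Protocol treatment must start within 14 business days of registration to the study". No text says which statement governs, and the table schedules no tumor measurement on Cycle 1 Day 1.

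For laboratory tests, the 6.2 lead-in reads "All screening labs must be performed within 14 days prior to registration unless otherwise stated". The asterisk footnote reads "Screening labs to be obtained within 14 days of initiation of therapy", and inclusion criterion 3.1.6 requires "Adequate hematologic, renal and hepatic function within 14 days prior to administration of study treatment as defined below".

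**The concern.** The baseline sum of target-lesion diameters is the reference for the primary endpoint: under 7.1.4.1 a partial response is a decrease of at least 30% from it. PFS runs from the start of treatment (2.4 and 7.1.6). If the tumor grows between the scan and the first dose, that growth is charged to the treatment. The patient must shrink by more than 30% from the size at first dose to be scored a responder. At first restaging, where the baseline is the only earlier sum available, part of the 20% increase that defines progression may already have happened before treatment.

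The decision rules in 11.2 turn on single patients. Cohort 1 stops with 1 or fewer responders of 16 and needs at least 5 of 26; cohort 2 stops with 0 of 13 and needs at least 4 of 27. One partial response missed because of an old baseline could change a decision. Section 6.1 also admits scans done for clinical reasons before consent, so scans near the early end of the window are foreseeable.

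**Working it through.** The plan states no maximum scan age at first dose under the registration rule, so there is no figure to reproduce.

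**Step 1: length of 14 business days.** Counting 14 business days after registration, with no public holiday, gives 18 calendar days for a Monday registration and 20 for Tuesday to Friday.

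**Step 2: scan age at first dose under the registration rule.** Maximum age = 28 + gap.

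- Monday: 28 + 18 = 46 days.
- Tuesday to Friday: 28 + 20 = 48 days.
- Limit in 7.1.3 and the asterisk footnote: 28 days, so the excess is 18–20 days.

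Sensitivity: one weekday holiday within the gap gives 49 days for a weekday registration. Counting the registration day as business day 1 gives 45–47 days.

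**Step 3: effect on the response threshold.** The documents give no growth rate. Assume that the target sum grows linearly by 5–20% per 30-day month between scan and first dose. If *g* is the proportional growth since the scan, a sum 30% below baseline lies 1 − 0.70/(1 + *g*) below the pre-dose size.

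| Scan age | Growth per month | *g* | Shrinkage needed from pre-dose size |
|---|---|---|---|
| 28 days | 5% | 0.05 × 28/30 = 0.047 | 1 − 0.70/1.047 = 33% |
| 28 days | 20% | 0.20 × 28/30 = 0.187 | 1 − 0.70/1.187 = 41% |
| 48 days | 5% | 0.05 × 48/30 = 0.080 | 1 − 0.70/1.080 = 35% |
| 48 days | 20% | 0.20 × 48/30 = 0.320 | 1 − 0.70/1.320 = 47% |

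The increment due to the conflict is 35 − 33 = 2 points at slow growth and 47 − 41 = 6 points at fast growth. Compound growth gives nearly the same answer (35–48% at 48 days).

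**Step 4: effect on first restaging.** For a 20% increase to have accrued before first dose, monthly growth must reach 20%/(48/30) = 12.5% with a 48-day-old scan, against 20%/(28/30) = 21.4% with a 28-day-old scan. If treatment then only halted growth, and the 5 mm absolute minimum was met, such a patient would be scored as progressing at first restaging.

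**The case against.** The strongest reply is that the rules are nested. A pre-registration scan within 28 days of first dose is also within 28 days of registration, so a site can satisfy every statement at once. Section 7.1.3 is absolute and the asterisk footnote repeats its limit. Read as a whole, the protocol makes a 48-day-old scan a deviation. This stands, and a reader should not infer that the protocol permits such a scan. It does not remove the inconsistency: the table's leading rule, worded as a requirement, accepts a baseline that 7.1.3 rejects, and no text ranks the two.

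A reader might also infer that the looser rule is the one applied, because documents are reviewed at registration. Section 4.0 does not support that. It has the site determine eligibility and the registrar review the Eligibility Worksheet and source documents, without saying which window is checked. Sites must already work to the first-dose date for criterion 3.1.6 and the pregnancy test.

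A third tempting reading is that eligibility laboratory tests could be 14 + 18 = 32 to 14 + 20 = 34 days old. The lead-in's own exception clause defers to rules stated elsewhere, and both 3.1.6 and the asterisk footnote count from treatment, so tests that old would fail 3.1.6. Blood count, chemistry and creatine phosphokinase are also repeated on Cycle 1 Day 1. What remains for laboratory tests is untidy wording.

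Finally, the bias is conservative: a lowered response rate cannot raise the chance of a false positive result against the 9% and 5% reference rates. That is correct. The cost is lost power and a response estimate that is too low.

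**Conclusion.** The imaging window is inconsistent and should be corrected. Under the registration rule a scan can be 46–48 days old at first dose, against the protocol's own limit of 28. On the assumed growth of 5–20% per month, the conflict raises the shrinkage needed for a partial response by about 2–6 percentage points.

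It would be wrong to count only the 20 excess days and compare the resulting 32–38% with 30%. Response is measured from the baseline sum, so all growth since the scan counts, and a compliant 28-day-old scan already requires 33–41%.

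The 2–6 points are a worst case: a scan on the earliest day allowed and treatment on the last. They rest on an assumed growth rate, and the downward direction rests on the sum growing between scan and first dose. The number of patients affected cannot be estimated from the documents. The effect on PFS is mainly at first restaging, because later progression is judged against the smallest sum since treatment started. The sample size calculation is not affected.

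**What to change.** In the 6.2 lead-in and in footnote c, replace the registration anchor for imaging with the treatment-start limit already in the asterisk footnote and 7.1.3. A scan older than 28 days at first dose is then repeated, and the repeat supplies the baseline sum. Maximum scan age becomes 28 days whatever the gap between registration and treatment.

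For consistency, align the 6.2 laboratory sentence with 3.1.6 and the asterisk footnote; this is wording only. Recording a planned first-dose date at registration would help sites see a late start coming, but is optional.

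The cost is a wording change and an occasional repeat scan, which 7.1.3 already requires.

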Key Exclusion Criteria	
 
• Prior therapy with PARP inhibitor
 
• Prior therapy with trabectedin
 
• Additional active malignancy or treatment for alternative cancer (excluding non-melanoma skin cancer) requiring treatment within the past two years
 
• Pregnant or breastfeeding women
 
• Known hypersensitivity to trabectedin
 

Study Product(s), Dose, Route, Regimen	Olaparib 150 mg PO BID continuously Trabectedin 1.1 mg/m  IV every 21 days
Duration of Administration	Treatment consists of 21-day cycles. Therapy will continue until disease progression or patient meets one of the off-study criteria for a maximum of 18 months.
Reference Therapy	No comparator. Historical controls of single agent trabectedin in soft tissue sarcoma.
Statistical Methodology	
A Simon Minimax two-stage design is utilized for this study. Based on currently available phase III data, the ORR for LMS/LPS subgroup to trabectedin monotherapy is 9%. We will target a response rate (RR) of 25% with combination trabectedin and olaparib. In cohort 2, the ORR is approximately 5% with trabectedin monotherapy. We will target a RR of 20% for this combination. This trial is designed with a type 1 error of 10% in cohort 1 and 5% in cohort 2 with a power of 80%.
 
Cohort 1: 16 patients will be enrolled in stage 1. If <math>\leq 1</math> patient has an objective response, we will terminate the study. If <math>> 1</math> objective response, an additional 10 patients will be enrolled. If <math>\geq 5</math> of 26 patients have an objective response, we will declare the combination as promising and worthy of further study.
 
Cohort 2: 13 patients will be enrolled in stage 1. If 0 patients have an objective response, we will terminate the study. If <math>\geq 1</math> objective response, an additional 14 patients will be enrolled. If <math>\geq 4</math> of 27 patients have an objective response, we will declare the combination as promising and worthy of further study.

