### 2.4 Endpoints

The primary endpoint is objective response (CR + PR) as based on RECIST 1.1 criteria anytime within a minimum of 18 months after start of treatment but no more than 2 years from registration. Disease response will be assessed after 2 cycles ( $\pm$  7 days), then every 3 cycles thereafter.

Secondary endpoints include progression-free survival as time from start of treatment to progression or death, or censored at the date of last tumor assessment if no progression and alive; overall survival, as time from start of treatment to death, or censored at the date of last follow-up if alive and occurrence of adverse events as graded by CTCAE v5.0.

Exploratory endpoints include the presence of mutations in DNA repair genes identified by next generation sequencing, presence of DNA repair defects identified by IHC changes in novel cardiovascular biomarkers.

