## 5.2 Toxicities and Dosing Delays/Dose Modifications

Any patient who receives treatment on this protocol will be evaluable for toxicity. Each patient will be assessed for the development of toxicity according to the Time and Events Table (Section 6.2). Toxicity will be assessed according to the NCI Common Terminology Criteria for Adverse Events (CTCAE), version 5.0. Dose adjustments should be made according to the system showing the greatest degree of toxicity. Any toxicity observed during the course of the study could be managed by interruption of the dose of study treatment or dose reductions. Repeat dose interruptions are allowed as required, for a maximum of 4 weeks on each occasion. If the interruption is any longer, the study team must be informed. Once dose is reduced, escalation is not permitted

Table 1. Dose Level Reductions of Trabectedin and Olaparib

Dose Levels	Trabectedin	Olaparib
1 (starting)	1.1 mg/m 	150 mg BID
-1	0.94 mg/m 	100 mg BID
-2	0.8 mg/m 	

Criteria for start of new cycle:

- Platelet  $\geq$  100,000/microliter
- Absolute neutrophil count  $\geq$  1000/microliter
- Hemoglobin  $\geq$  9g/dl
- Total bilirubin  $\leq$  1.5 upper limit of normal (ULN)
- Aspartate aminotransferase (AST) and alanine aminotransferase (ALT)  $\leq$  2.5 x ULN
- Alkaline phosphatase (ALP)  $\leq$  2.5 x ULN
- Creatine phosphokinase (CK)  $\leq$  2.5 x ULN
- All non-hematologic toxicities considered related to study treatment must be  $\leq$  grade 2
- Absence of any subjectively intolerable grade 2 adverse event not controlled by supportive therapy

If a patient does not meet criteria to initiate a new cycle of treatment within 28 days of initial medication hold, or requires more than two dose reductions of trabectedin or one dose reduction of olaparib, they should be removed from study treatment.

For hematologic toxicities which meet parameters for dose hold, medication should be held per guidance below. Medication should be resumed at the reduced dose designated below. If AE is recurrent/persistent despite dose reduction as specified below, drug should be discontinued.

Table 2. Criteria for Dose modification of Thrombocytopenia, Neutropenia and Leukopenia

Laboratory Result	Dose Adjustments

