### **11.3 Data Analyses Plans**

To address the primary objective, the overall response rate will be calculated as the proportion (and exact binomial 95% confidence interval) of patients with complete or partial response as defined by RECIST 1.1, within each cohort.

To address the secondary objectives:

- a. Progression free survival (PFS) will be calculated by the Kaplan-Meier method with errors according to Peto, within each cohort. Median and 6-month PFS will be estimated along with their 95% confidence intervals.
- b. Overall survival (OS) will be calculated by the Kaplan-Meier method with errors according to Peto, within each cohort. Median, 1- and 2-year OS will be estimated along with their 95% confidence intervals.
- c. The frequency and rates of adverse events occurring in at least 5% of participants and rates of grade 3-5 adverse events will be tabulated by system organ class and preferred term using Common Terminology Criteria of Adverse Events (CTCAE), within each cohort.

To address the exploratory objectives:

- a. The frequency and proportion of alterations in tumor sequencing will be summarized within each cohort.
- b. The frequency and proportion of alterations in DNA damage repair pathways will be summarized within each cohort.
- c. Changes in levels of novel cardiovascular biomarkers will be summarized and compared to clinical and echocardiographic cardiotoxicity.

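### Restaging scans are counted in cycles while 6-month PFS is read in calendar time, so a cumulative cycle delay beyond about two weeks can move the deciding scan past 6 months

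*Combined protocol and SAP*

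**What the plan says.** - **Scan schedule.** Footnote c to the Time and Events Table (6.2) states "Restaging scans will be repeated at C3D1", then every 3 cycles, with a window of 7 days either side. Section 2.4 gives the same rule: a first assessment after 2 cycles, "then every 3 cycles thereafter". Both count cycles, not weeks.
- **Cycle length.** The Study Synopsis says "Treatment consists of 21-day cycles".
- **PFS.** Section 2.4 measures PFS from start of treatment to progression or death, with censoring at the last tumor assessment. Section 11.3 uses Kaplan-Meier within each cohort: "Median and 6-month PFS will be estimated along with their 95% confidence intervals". It has no sensitivity analysis for late or uneven assessment times.
- **Holds.** Section 5.2 states "Repeat dose interruptions are allowed as required, for a maximum of 4 weeks on each occasion". It also removes a patient from treatment if a new cycle cannot start within 28 days of the initial hold.
- **Provision for delay.** Footnote c adds "If clinical concerns for progression or significant delays in cycle length, imaging assessment may be obtained early at the discretion of the treating physician". After such a scan, imaging again continues on a 3-cycle count. The footnote also asks for an end-of-treatment scan if progression has not already been shown on imaging.

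**The concern.** A landmark estimate at 6 months depends on when patients were last scanned before 6 months. If the scan that should decide a patient's status slips past the landmark, a progression that has already happened is recorded later, and the patient counts as progression-free at 6 months. Because scans move with cycle starts, the slip depends on toxicity and recovery rather than on a common calendar.

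Delays are foreseeable. Section 1.3 reports thrombocytopenia and prolonged neutropenia as the dose-limiting toxicities of this combination in phase 1b, and section 5.2 requires blood counts and liver values to recover before a new cycle. What is at stake is an upward error in a named secondary endpoint, in a single-arm trial with no concurrent arm to share it.

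**Working it through.** The documents give no target, null value or precision for 6-month PFS, so there is no stated figure to reproduce.

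**Step 1. Slack before the landmark.** Scan day of cycle k, day 1 = (k − 1) × 21 + cumulative delay.

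- C3D1: 2 × 21 = day 42 (week 6)
- C6D1: 5 × 21 = day 105 (week 15)
- C9D1: 8 × 21 = day 168 (week 24)
- C12D1: 11 × 21 = day 231 (week 33)

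Six months = 6 × 30.4375 = 182.6 days. Slack = 182.6 − 168 = 14.6 days. With the scan 7 days late or early, the slack is 7.6 or 21.6 days, so roughly 1 to 3 weeks. Spread over the 8 cycles before C9, the nominal slack is 14.6 / 8 = 1.8 days per cycle.

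**Step 2. What a delayed patient carries.** Once the C9 scan passes day 182.6, the last scan before the landmark is the C6 scan. It is on day 105 if the whole delay comes after C6, and on day 105 + 28 = 133 if a single 28-day delay comes before it.

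**Step 3. Size.** Assume exponential PFS, S(d) = 0.5^(d / (30.4375 × median)), with progression found only at scheduled scans. The Kaplan-Meier value at 6 months is then S at the last scan before 6 months. The medians are the trabectedin-alone figures in section 1.2.

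| | Median 4.2 months | Median 5.6 months |
|---|---|---|
| True value, day 182.6 | 37.1% | 47.6% |
| On schedule, day 168 | 40.2% | 50.5% |
| Delayed, C6 scan on day 133 | 48.6% | 58.2% |
| Delayed, C6 scan on day 105 | 56.6% | 65.2% |

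**Step 4. Cohort effect.** Inflation over the on-schedule reading = f × [S(C6 scan day) − S(168)], where f is the share delayed past the slack. The documents do not give f, so a range is assumed.

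| f | Median 4.2 months | Median 5.6 months |
|---|---|---|
| 10% | 0.8 to 1.6 points | 0.8 to 1.5 points |
| 25% | 2.1 to 4.1 points | 1.9 to 3.7 points |
| 50% | 4.2 to 8.2 points | 3.9 to 7.4 points |

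For example, at f = 25% and median 4.2 months: 0.25 × (56.6 − 40.2) = 4.1 points.

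**Step 5. Delays inside the slack.** A 14-day delay puts the C9 scan on day 182, where S = 37.3% at median 4.2 months. That is closer to the true 37.1% than the on-schedule 40.2%. Delays that stay inside the slack do not inflate the estimate.

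**The case against.** **The protocol already deals with delay.** Footnote c names significant delays in cycle length as a trigger for early imaging, separately from clinical concern. It would be wrong to say that the plan is silent, or that early scans depend only on how the patient looks. What remains is that the scan is optional, significant is not defined, and the count then goes back to cycles.

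**A dose hold is not a cycle delay.** Most of the hematologic rules in section 5.2 interrupt olaparib only, and several allow restart within the cycle. The 28-day limit runs from the initial hold. A hold from day 8 must end by day 36, so the cycle due on day 22 slips by at most 14 days, just inside the nominal slack; a hold from day 15 allows at most 21 days. Single delays of 3 to 4 weeks are therefore near the permitted maximum. This stands against any claim that large slips are typical. It does not remove the mechanism, because repeated shorter delays add up, liver abnormalities hold both drugs, and a new cycle still waits for counts to recover.

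**The effect is small beside the sampling error.** For an estimate of 40% in 26 patients, the 95% half-width is about 1.96 × √(0.4 × 0.6 / 26) = 19 points. That is correct and limits the priority, although a one-directional error is not reflected in the confidence interval.

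**Stronger readings that do not hold.** A reader might infer that the bias rises steadily with toxicity; step 5 shows that delays inside the slack reduce it. A reader might also infer that every delayed patient reads 57%, but that needs the delay to fall after C6. Finally, a reader might infer that the comparison with trabectedin alone is tilted toward the combination. The documents do not give the scan schedules of the reference trials, and section 11.3 plans no formal comparison of PFS.

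**Conclusion.** The mismatch between cycle-based scans and a calendar-based landmark is real and follows from the protocol's own text. A cumulative cycle-start delay beyond 14.6 days (about 1 to 3 weeks with the scan window) can leave the 6-month reading resting on the C6 scan.

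At median 4.2 months, the cohort estimate is raised by roughly 1 to 2 points if 10% of patients are delayed past the slack, 2 to 4 if 25%, and 4 to 8 if 50%. For each assumed share these are upper bounds, because unscheduled scans, end-of-treatment scans and deaths register some events earlier. They rest on exponential PFS, a single delay and delay shares that the documents do not supply. The effect on median PFS was not quantified.

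PFS is a secondary endpoint that is estimated without a decision rule. The Simon go/no-go decision rests on objective response and is not affected by this mechanism. The point is an optional, cheap improvement.

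**What to change.** In section 2.4 and in footnote c to the Time and Events Table, keep the protocol's own intervals but count them from C1D1. Suggested wording: *restaging at week 6 and every 9 weeks thereafter, ±7 days, counted from C1D1 regardless of dose holds or cycle number; unscheduled scans remain allowed and do not reset the calendar.*

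Patients on schedule are scanned on the same days as now. With the change, delayed and undelayed patients alike read S(168): 40.2% at median 4.2 months and 50.5% at median 5.6 months.

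Costs and limits:

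- For delayed patients, scans no longer coincide with cycle-day visits, the C3D1 biomarkers or the three-cycle echocardiogram.
- Their scans come earlier relative to cycles received, and the first may precede completion of 2 full cycles. The same scans feed the primary response assessment, so the reference in section 2.4 to assessment after 2 cycles must be reworded to match.
- About 3 points of upward reading remain (40.2% against 37.1%), because the last scan before 6 months is still at week 24. A scan at week 26 would read 37.3%, but that would change the protocol's intervals and is not needed to remove the dependence on delays.
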